9.3. Approval from the facility's ethics review committee (institutional review board)

For participation in the study to be confirmed, the document describing the study procedures, as well as the explanation given to the patient and/or their family member(s), must both be confirmed by the facility's ethics review committee or IRB

10. DATA COLLECTION

The following documents are to be submitted by fax to the Data Coordinating Center ([contact]). They may also be sent by post, in which case the facilities are to retain the original documents and send copies to the Data Coordinating Center. When submitting documents, all names that might permit identification of the patient concerned should be changed to initials. The registration number should be clearly indicated on the form. DVDs or videotapes containing the echocardiographic data should be sent by post to the Data Coordinating Center. If the echocardiographic data contain information permitting identification of the patient (patient name or ID), this information will be masked by the Data

Coordinating Center and rerecorded so as not to permit patient identification, after which the original data will be destroyed.

RAISE Study Data Coordinating Center

Department of Clinical Investigation and Research Unit, Gunma University Hospital

[name]

Tel: [name] Fax: [name]

10.1. Documents for patient registration, etc.

- 1) Form for facilities to request permission to participate in the study
- 2) Form to request patient assignment by fax (if online assignment is impossible)
- 3) Data sheet
- 4) Express form for preliminary reports of adverse events
- 5) Form for full report of adverse events
- 6) DVD or videotape for recording and submitting patient echocardiogram findings

10.2. Data Cleaning

The Data Coordinating Center will check the registration information and submitted documents. If there are any questions regarding this information, the Data Coordinating Center staff will contact the attending physician by email, fax, or telephone to request necessary clarifications. As for the treatment protocol, any cases in which the treatment or laboratory or echocardiographic examinations may have diverged from the pre-planned acceptable ranges will be reported to the RAISE Study Office for evaluation and judgment. Obvious violations from the protocol will immediately be reported to the RAISE Study Group Principal Investigator ([name]), who will quickly deal with such cases.

11. REPORTING ADVERSE EVENTS

Adverse events should be reported by fax to the Data Coordinating Center.

11.1. Adverse events that must be reported

11.1.1. Adverse events that must be reported immediately

All patient deaths that occur during the protocol treatment or during the 30-day period immediately after the last day of treatment (regardless of whether this was a result of adhering to the treatment protocol)

11.1.2. Adverse events that must be reported at earliest convenience

- 1) Cases of shock that appear to be related to the administration of the study medication
- 2) Cases in which the patient contracted a severe infectious disease
- 3) Hyperglycemia or hypertension accompanied by clear symptoms
- 4) A body temperature <35.0°C
- 5) The appearance of eye disorders such as cataracts or glaucoma
- 6) Thromboembolism
- 7) Severe hemorrhage
- 8) Other important clinical phenomena not in the above list but judged to be potentially important should be shared with the RAISE Study Group Principal Investigator, the RAISE Study Office, and other participating facilities

11.2. The duties and procedures of reporting to facility chief investigators participating in this study

There are 2 methods of reporting adverse events: express and standard reporting, which are explained below.

11.2.1. Express report

When an adverse event occurs that requires express reporting, the attending physician should report it to the facility chief investigator as quickly as possible. If it is not possible to contact the chief investigator, the attending physician must report the adverse event. The adverse event shall be reported to the RAISE Study Group Principal Investigator in the following manner.

Initial report:

Within 72 hours of the occurrence of an adverse event, the facility chief investigator will fill in the necessary information in the Adverse Event Preliminary Express-Report Form. After contacting the RAISE Study Office, the facility chief investigator will fax this form directly to the Data Coordinating Center. Because this report should be submitted as quickly as possible, any information requested on the form that is not available at the time it is completed should be left blank. After receiving this preliminary report from the facility, the Data Coordinating Center will then inform both the RAISE Study Office and the RAISE Study Principal Investigator of the details they have received concerning the adverse event.

Secondary report:

The facility chief investigator will then complete the Adverse Event Report Form (Second Express Report), with the more detailed information requested on the form, and fax it to the Data Coordinating Center within 15 days after the appearance of the event. After receiving it, the Data Coordinating Center will then inform the RAISE Study Office and the RAISE Study Principal Investigator of this additional information as quickly as possible. The RAISE Study

Principal Investigator will then quickly inform the Efficacy and Safety Review Board of the event. They will discuss its significance with regard to the progress of the research and future of the RAISE study.

11.2.2. Standard report

Within 15 days of the appearance of the adverse event, the facility chief investigator will complete the Adverse Event Report Form (Final Report) with the required information and fax it to the Data Coordinating Center. After receiving it, the Data Coordinating Center will then inform the RAISE Study Office and the RAISE Study Principal Investigator of any further relevant information as quickly as possible.

11.3. Responsibilities of the RAISE Study Principal Investigator and RAISE Study Office

11.3.1. Judgment of suspension and emergency information to the facilities

When the RAISE Study Principal Investigator receives information from an express report regarding adverse events from facility chief investigators, he will determine the urgency and importance of this information, evaluate its effect on the future of the study, and consider approaches and remedies for it. If immediate action is required, he may contact the Data Coordinating Center and/or facility concerned by telephone; however, this will be followed, as quickly as possible, with a written communication (fax, mail, or e-mail)

11.3.2. Reporting to the Efficacy and Safety Review Board

Once the RAISE Study Principal Investigator has received either the express or final report from a facility about an adverse event, he will determine, based on the list in section 11.1. above ("Adverse events that must be reported"), whether the reported adverse event is indeed one that requires reporting. If it is, after consulting with the RAISE Study Office, he will prepare a written report for the Efficacy and Safety Review Board regarding the event, within 15 days of having been informed of it, inform them of his opinions with regard to the event, and ask the Board to decide whether the clinical response to the event was suitable. This should include the results of his analysis of the adverse event report received from the medical facility, together with how he plans to deal with this information (including whether the study should be continued or terminated).

11.3.3. Analysis of adverse events based on regular monitoring

When regular monitoring is carried out, the RAISE Study Principal Investigator and RAISE Study Office will carefully review reports produced by the Data Coordinating Center regarding adverse events that have been reported, to ensure that no important information has been omitted and is thus still required from the medical facility concerned.

11.3.4. Analysis of the Efficacy and Safety Review Board

The Efficacy and Safety Review Board will inspect and analyze the content of all reports and state in writing its decisions on responses to adverse event to the RAISE Study Principal Investigator, including whether the patient(s) concerned should be removed from the study and whether the treatment protocol should be modified or not.

12. STATISTICS

12.1. Principal analyses and criterion

The main goal of the present study is to determine whether, as compared with standard IVIG treatment, treatment with IVIG plus PSL results in a significant reduction in the primary endpoint, i.e. the incidence of CAA during the study period. To test the null hypothesis (namely, that the incidence of such complications will be the same in both groups), Fisher's exact test will be used to compare all applicable cases in the 2 groups. Because it is possible that the trial treatment could result in worse outcomes than standard treatment, all testing will be 2-sided. The significance level for all tests will be 5% (2-sided).

If statistical analysis reveals that the incidence of CAA during the study period is significantly lower in the trial treatment group than in the standard treatment group, the conclusion will be that the trial treatment with IVIG plus PSL is the more effective treatment. If no such significant decrease is found, the conclusion will be that treatment with IVIG remains the standard treatment for KD.

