12.3. Interim analysis and early termination of study

12.3.1. Purpose and timing of the interim analysis

One interim analysis is planned to evaluate whether the study is achieving its principal objectives. The purpose of this interim analysis will be to decide on the suitability of continuing to enroll patients in the study. If it is determined that the principal objectives of the study have been achieved, then the study will be terminated and its results reported at conferences and published in relevant journals as quickly as possible.

The interim analysis will be started after the first year of the study has been completed, using the initial monitoring data accumulated since the start of the study. In the event that 200 patients have not yet been enrolled in the study at 1 year after initiation of the study, the interim analysis will be done when data for 200 patients become available. Finally, as a rule, patient enrollment will continue while the interim analysis is being conducted.

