12.3.2. Method of interim analysis

The interim analysis will be carried out by the staff of the RAISE Study Statistical Center. To keep overall α error of the RAISE study below 5%, the Lan-DeMets α -spending function³⁶⁾ with the O'Brien-Fleming monitoring boundaries was used to adjust for multiple comparisons. Differences in values between the 2 study groups will be analyzed to determine if they are statistically significant or not. If the interim analysis reveals a lower rate of CAA during study period in the group receiving IVIG plus PSL as compared with the group receiving standard IVIG and Fisher's exact test yields a p value <0.0034, this will be considered sufficient statistical evidence to accept the study's main hypothesis and, barring other important considerations, the study will, in principle, be terminated.

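### Section 12.1's flat 5% level for all tests contradicts the alpha-spending plan in 12.3.2, which implies a final primary level of about 0.0489

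*Protocol*

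**What the plan says.** Protocol 12.1 names Fisher's exact test for the primary endpoint, CAA during the study period, and then says: "The significance level for all tests will be 5% (2-sided"). Its next paragraph rests the trial's conclusion on whether that test is significant. Section 12.2 sizes the trial at a two-sided 5% and does not mention the interim look.

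Section 12.3.1 says: "One interim analysis is planned to evaluate whether the study is achieving its principal objectives". The look follows the first year, but if 200 patients have not been enrolled by then, "the interim analysis will be done when data for 200 patients become available".

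Section 12.3.2 gives the purpose of the adjustment: "To keep overall α error of the RAISE study below 5" per cent. It names the Lan-DeMets spending function and says that O'Brien-Fleming "monitoring boundaries was used to adjust for multiple comparisons". The trial may stop if there is "a lower rate of CAA during study period in the group receiving IVIG plus PSL" and Fisher's "exact test yields a p value <0.0034". No section states a reduced level for the final analysis.

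**The concern.** An alpha-spending plan divides one error budget between the looks. Whatever is spent at the interim has to come off the final test, so the final nominal level must lie a little below 5%. The only level the protocol gives for the final primary test is the unreduced 5% of 12.1.

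What is at stake is which threshold decides the primary claim. A final p value between 0.0489 and 0.05 would be significant under 12.1 and not significant under the boundary implied by 12.3.2. Section 12.1 attaches opposite conclusions to those two outcomes. If the threshold is settled only after the data are seen, either choice will look driven by the result.

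**Working it through.** **Inputs.** Overall two-sided alpha 0.05 (12.1, 12.3.2); one interim look with cut-off 0.0034 (12.3.1, 12.3.2); interim at 200 patients (12.3.1); final total 392, or 352 before the dropout allowance (12.2); Fisher's exact test at both looks (12.1, 12.3.2); CAA rates 18% and 8% (2.3.3). Information is counted in patients, with equal arms.

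**1. Reproduce the interim cut-off.** The O'Brien-Fleming-type spend, applied to each side at 0.025, is 4 × [1 − Φ(2.2414/√t)]. With t = 200/392 = 0.5102, √t = 0.7143 and 2.2414/0.7143 = 3.138. The spend is 0.00340, which is the protocol's 0.0034. The intended design can therefore be identified.

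**2. Overall alpha with 0.05 at the end.** The interim and final statistics are bivariate normal with correlation √t = 0.714. The critical values are 2.929 (p = 0.0034) and 1.960 (p = 0.05).

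- Two-sided interim: P(|Z1| > 2.929 or |Z2| > 1.960) = 0.0511.
- Interim stop for benefit only, as 12.3.2 words it: 0.0505.

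The excess over 0.05 is 0.11 and 0.05 percentage points. It is less than the simple sum 0.0034 + 0.05 = 0.0534 would suggest, because the looks are correlated.

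**3. Final level that the plan implies.** Solving for an overall 0.05, with 0.0034 already spent at t = 0.5102, gives a final two-sided nominal level of 0.0489 (|Z| ≥ 1.970).

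**4. Realised error with the specified test.** Exact enumeration of the two-look Fisher test, with 100 then 196 per group, two-sided rejection at both looks, and 0.0034 then 0.05:

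| Common CAA rate | Overall size |
|---|---|
| 5% | 0.029 |
| 8% | 0.032 |
| 13% | 0.036 |
| 18% | 0.038 |
| 30% | 0.040 |
| 50% | 0.039 |

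All are below 0.05.

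**5. Can the two thresholds disagree?** Yes. At 176 per group, 28 against 15 patients with CAA (15.9% against 8.5%) gives Fisher p = 0.0498, which passes 0.05 and fails 0.0489. It is rare. At 18% against 8%, two-look Fisher power with final levels of 0.05 and 0.0489 is 76.5% and 75.9% at 176 per group, and 81.2% for both at 196 per group (a difference of about 0.002 point).

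**6. Separate check: the fixed 0.0034.** The same spending formula gives 0.0059 at 200/352 and 0.0100 at 250/392, with final levels of 0.0481 and 0.0469. Keeping 0.0034 at those fractions underspends. With a final 0.05, the nominal overall alpha would then be 0.0509 and 0.0506, both below the 0.0511 of step 2.

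**The case against.** A reader might infer that the trial's type I error really exceeds 5%. The documents do not support that. They fix Fisher's exact test at both looks, and step 4 shows that its realised error stays clear of 5% even with a final 0.05. The 0.0511 describes the nominal boundaries, not the error rate of this test. This part of the objection stands in full.

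It can also be said that 12.3.2 already governs. The spending function, the single look and the overall alpha together determine the final boundary, 12.1 can be read as a general level to which the 0.0034 is already an exception, and the exact final level is often left to a statistical analysis plan. The first part is fair, and it makes this a contradiction between two sections rather than a settled plan to overspend. The last part does not answer the point. The protocol does not leave the level open: it states 5% for all tests in the section that defines the primary test. An analysis plan that used 0.0489 would depart from 12.1.

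Finally, a reader might take the fixed 0.0034 as a further source of inflation. It is not, because a later look with 0.0034 underspends. A look beyond 200 patients is also unlikely: it needs more than 200 enrolled in the first year, against 392 over three years, or about 131 a year.

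**Conclusion.** The contradiction is real and lies in the primary decision rule: 12.1 states a final level that the spending plan in 12.3.2 rules out. Its size is small. The nominal overall alpha is 0.0511 (0.0505 with a benefit-only stop) instead of 0.05, and the implied final level is 0.0489 instead of 0.05. It is an error in the stated threshold and not an actual breach of 5%, since the realised Fisher error is about 0.032 to 0.040 for common rates of 8% to 50%.

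The nominal figures assume a look at 200 of 392, information proportional to patients, equal arms and all 392 evaluable. With 0.0034 held fixed, the final level moves only from 0.0488 at t = 0.50 to 0.0491 at t = 200/352, so the conclusion does not depend on the exact fraction.

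**What to change.** In 12.1 and 12.3.2, state that the final primary test uses the alpha remaining after the interim: a two-sided nominal level of 0.0489 if the look is at 200 of 392 patients. In 12.1, limit the 5% to the overall error rate of the primary endpoint and to the secondary tests.

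As a separate minor addition, state in 12.3.2 that both boundaries are recomputed from the spending function at the actual information fraction, with 0.0034 given as the value planned for 200/392.

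The cost is a few sentences, settled before any unblinded comparison. With Fisher's test the power loss is under 0.1 point at 196 per group and about 0.6 point at 176 (76.5% − 75.9%). By the normal approximation, power at 196 per group goes from 84.0% to 83.8%, and the sample size before dropout from 177 to 178 per group.

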12.2. Target number of subjects/ registration period/ follow-up periods

As mentioned in the background of the study (section 2.3.3., "Clinical hypotheses and reason for number of registrants"), the rate of CAA in the IVIG group is expected to be the same as in previous studies of this treatment, ie, approximately 18%. The study design has been established to determine whether the trial treatment (IVIG plus PSL) can achieve at least an additional 10% absolute reduction in the incidence of CAA during the study period, i.e. reduce the incidence rate to 8% or less. If the study requires a 3-year registration period and a 1-month follow-up period, and α is equal to 5% (2-sided) with a statistical power of 80%, the number of cases required for each group will be 176, for a total of 352 in the 2 groups. If a 10% drop-out rate is assumed, the final enrollment numbers are as follows.

Target number of subjects: 196 per group, for a total of 392 patients.

Registration period: 3 years. Follow-up period: 1 month after enrollment.

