2.3.3. Clinical hypotheses and reason for number of registrants

The principal hypothesis of the present study is that patients with severe KD who receive the study treatment (IVIG with PSL) will have a significantly lower incidence of CAA during the study period as compared with the group receiving standard treatment (IVIG). If this does indeed prove to be true, then initial treatment with IVIG plus PSL will be judged to be more effective.

The target enrollment was set using data obtained from 1123 consecutive KD patients from August 2000 to August 2007 at 13 hospitals in Gunma and Saitama prefectures, Japan. ²³⁾ Eight KD patients who presented with CAA at admission and 109 KD patients with missing values were excluded from this study. Thus, data from 1006 KD patients (IVIG group n=896, IVIG+PSL group n=110) were analyzed. Of the 110 patients in the IVIG+PSL group, 90 were participants of a previously reported randomized trial. ¹⁸⁾ The other 20 patients were given IVIG+PSL according to the attending doctor's recommendations, except for 1 patient

whose parents desired treatment with IVIG+PSL. The table below shows clinical and coronary outcomes in the high-risk group.

	IVIG (n=298)	IVIG+PSL (n=48)
Nonresponse to treatment	51.7	20.8
Incidence of coronary artery abnormality during 1 month	18.1	6.3
Incidence of coronary artery abnormality at 1 month	8.4	4.2

The primary endpoint of the RAISE Study is to assess whether the incidence of CAA in the study treatment is significantly lower than that of the standard treatment during the study period. Based on the above data, the required sample size was calculated with the assumption that IVIG plus PSL would reduce the fraction of patients with CAA during the study period from 18% to 8%. With a 2-sided test, an α level of 0.05, and a power of 80% and assuming that 10% of the patients would not complete the study, a total sample of 392 patients would be required. Analyses were intent-to-treat. Fisher's exact test was used to test the null hypothesis, i.e. that the incidence of CAA would be equal between the 2 treatment groups during the study period.

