6.2. Random assignment and assignment adjustment factors

Dynamic random assignment of patients to their respective groups will be done using the minimization method at a 1:1 ratio. The adjustment factors include sex, age, and institution, classified by method of additional rescue therapy (Group A; IVIG retreatment only, Group B; IVIG retreatment and/or conventional dose of PSL, Group C; IVIG retreatment and/or pulsed dose methylprednisolone with or without subsequent PSL, Group D; IVIG retreatment and/or conventional dose of PSL and/or pulsed dose methylprednisolone with or without subsequent PSL and/or infliximab).

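### The stated 80% power does not belong to Fisher's exact test: at 176 evaluable patients per group it has about 76.5%

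*Protocol*

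**What the plan says.** Section 2.3.3 sizes the trial on the assumption that adding prednisolone would "reduce the fraction of patients with CAA during the study period from 18% to 8"%. With a two-sided 5% test, 80% power and 10% of patients not completing, "a total sample of 392 patients would be required". The same paragraph names Fisher's exact test for the primary hypothesis and says that analyses are by intention to treat.

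Section 12.2 gives the step in between: "the number of cases required for each group will be 176, for a total of 352 in the 2 groups". The 10% drop-out allowance then raises this to 196 per group, 392 in total. Neither section names the sample size formula.

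Section 12.1 fixes the primary analysis: "Fisher's exact test will be used to compare all applicable cases in the 2 groups", two-sided at 5%. Section 12.3.2 uses Fisher's test again at the interim look, with a threshold of p<0.0034. Allocation under section 6.2 is 1:1.

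**The concern.** Section 2.3.3 puts the sample size, the 80% power and Fisher's exact test in one paragraph, so a reader takes the power to be that of the test. Fisher's test conditions on the total number of events. With discrete counts it rejects less often than its nominal 5% allows, so it needs more patients than a chi-square test for the same power. The figure of 176 leaves no room for this.

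The stake is the false-negative risk. Section 12.1 attaches a firm conclusion to a non-significant result: IVIG alone remains the standard treatment. If the true rates are 18% and 8% and 176 per group are evaluable, that conclusion would be reached wrongly in about 23.5% of trials (100% − 76.5%) rather than the stated 20%.

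**Working it through.** **Inputs.** Rates 18% and 8% (2.3.3, 12.2); two-sided α = 0.05 (12.1, 12.2); power 80% (2.3.3, 12.2); allocation 1:1 (6.2); drop-out 10% (12.2); Fisher's exact test (2.3.3, 12.1).

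**Step 1: reproduce the plan's figure.** Pooled chi-square formula without continuity correction, with mean rate 0.13:

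n = [1.96·√(2·0.13·0.87) + 0.8416·√(0.18·0.82 + 0.08·0.92)]² / 0.10²

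= [0.9322 + 0.3958]² / 0.01 = 176.36 per group.

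Rounded to the nearest whole number this is the protocol's 176; rounded up it would be 177. Drop-out: 176/0.9 = 195.6, so 196 per group and 392 in total, as stated.

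**Step 2: try other formulas.** Unpooled variance gives 173.6 and the arcsine formula 171.2. The continuity-corrected formula, the usual approximation for Fisher's test, is (n/4)·[1 + √(1 + 4/(0.10·n))]² with n = 176.36, which gives 195.8, or 196. This equals the enrolment target only by coincidence, because section 12.2 derives its 196 from 176 by the drop-out allowance.

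**Step 3: exact power of the named test.** All pairs of binomial counts were enumerated. The two-sided Fisher p-value sums all tables no more likely than the one observed, and the probability of p ≤ 0.05 was added up under 18% versus 8%.

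| Evaluable per group | Meaning | Fisher power |
|---|---|---|
| 176 | 10% lost from 196 | 76.5% |
| 186 | 5% lost | 78.6% |
| 191 | | 79.9% |
| 192 | 2% lost (4/196) | 80.1% |
| 196 | no loss | 81.1% |

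For comparison, the uncorrected chi-square test at 176 per group has an exact power of 81.0%.

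**Step 4: why the two tests differ.** The true two-sided size of Fisher's test at 176 per group is 3.6%, 3.5% and 3.0% at common event rates of 18%, 13% and 8%. The unused part of the 5% is what costs the power.

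**Step 5: the interim look.** The protocol gives only the interim threshold. If the final alpha falls to about 0.048 (an assumption), Fisher's power at the final look alone is about 75.8% with 176 per group and about 80.6% with 196.

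**The case against.** The best counter-argument is that 392 patients are to be enrolled and analysed by intention to treat, and that Fisher's test has 81.1% power with all of them. This is true as arithmetic, and it rules out the flat statement, which a reader might infer, that the design has 76% power. It does not rescue the stated figure. Section 12.2 defines 176 as the number required and uses the other 20 per group for drop-out. Section 5.3 withdraws patients whose information can no longer be obtained, and section 12.1 compares only applicable cases. So nothing guarantees that all 392 are analysed, and the same 20 patients cannot cover both drop-out and the choice of test.

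A second argument is that the gap is small beside the uncertainty in the planning rates. At 176 per group, Fisher's power is 68% for 17% versus 8%, 81% for 18% versus 7.5%, and 91% for the historical rates of 18.1% versus 6.3% in section 2.3.3. This stands, and it limits how serious the point is. It does not make 80% correct at the rates the protocol chose.

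Third, a reader might infer that the authors used a chi-square formula by mistake. The documents do not say so. The match with 176.36 is suggestive, but the shortfall follows from the stated number, rates, alpha and test alone.

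**Conclusion.** The point holds, as a modest error in a stated design property. At the 176 evaluable patients per group that section 12.2 ties to 80% power, Fisher's exact test has about 76.5%, a gap of 3.5 points. For 80% it needs 192 evaluable per group, 16 more than stated. The drop-out allowance therefore covers losses of about 2%, not 10%. These figures rest on true rates of exactly 18% and 8%, and on a final test at the full 5%. A final alpha near 0.048 would take the 76.5% to about 75.8% at the final look.

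Two stronger readings are not supported. The validity of the primary test is not in doubt: Fisher's test is conservative, so the type I error is protected. Nor does the mismatch show that Fisher's test is the wrong choice; it is a legitimate one, and only the power attached to it is misstated. The correction should be made, but the trial does not depend on it.

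**What to change.** In sections 2.3.3 and 12.2, restate the power as about 76% with 352 evaluable patients under two-sided Fisher's exact test (18% versus 8%), and about 81% only if all 392 are analysed. Name the formula or method behind the 176. This costs a sentence in each section and no patients.

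For scale, holding 80% under Fisher's test with 10% loss would need 192/0.9 = 213.3, so 214 per group or 428 in total. That increase is not needed to correct the statement.

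Replacing the primary test with the uncorrected chi-square test would bring the power in line with the sizing (81.0% at 176 per group). This is optional. It would also change the interim rule in section 12.3.2, which is written for Fisher's test, and it would have to be fixed before any unblinded data are seen.
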